**Secondary Aim: To examine mechanisms of drinking behavior changes following treatment.**

Hypothesis 2. Effect of active tDCS on drinks per drinking day at the 2-month follow-up will be mediated by greater mindfulness, greater inhibitory control and reductions in cue-reactivity, craving, and negative affect during treatment and at the post-treatment assessment. The effect of the “dose” of treatment, including session attendance and amount of mindfulness practice, on drinks per drinking day at 2-months will be mediated by greater mindfulness and inhibitory control and reductions in cue-reactivity, craving, and negative affect.

Hypothesis 3. Based on prior EEG studies of alcohol use disorder and mindfulness, we hypothesize significantly increased amplitude of the P3 (e.g., P300) component of the event-related brain potential (ERP) during cognitive inhibition and reduced P3 amplitude in response to alcohol cues in the active tDCS group at post-treatment, as compared to sham tDCS. Changes in ERPs among those who receive active tDCS with MBRP will be significantly associated with reductions in drinks per drinking day following treatment.

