## V. *Data Collection Procedures*

**Procedures.** Following phone screen, eligible participants will be invited to the Psychology Clinical Neuroscience Center (PCNC) for the baseline session, which includes being breathalyzed to ensure a breath alcohol concentration (BAC) of 0.0, pregnancy testing for fertile female participants, providing informed consent, completing a battery of self-report and behavioral measures, baseline EEG, and baseline stimulation session. Participants who have a BAC > 0.0 will be rescheduled, given snacks and water until their BAC is reduced to < 0.04 in accordance with NIAAA guidelines, and will be provided a taxi voucher. Participants will take part in the intervention for 8 two and a half hour sessions up to 8 weeks. At each 150-minute session, participants will undergo 30 minutes of initial assessment and verification of session eligibility (e.g., breathalyzer, withdrawal assessment, pregnancy tests, and self-report), 30 minutes of tDCS during a guided meditation practice followed by 90 minutes of MBRP session content. The overarching goal of the meditation is to help participants obtain greater mental clarity through training attention and awareness, decreasing emotional reactivity, and improving general well-being. All study participants will be assigned to the MBRP condition. All tDCS sessions will be double blinded with active and sham tDCS participants within all groups. Pilot testing of this protocol has demonstrated feasibility of combining active and sham tDCS within a single group, while maintaining the blind.

**Measures.** Table 1 provides the assessment schedule for the proposed study. Consistent with the Secondary Aim to understand the mechanisms of behavior change at multiple levels of analysis, we have included self-report and behavioral assessments of inhibitory control (NIH Cognition Toolbox, UPPS Impulsive Behavior Scale, Stop Signal Task), cue reactivity and craving (Penn Alcohol Craving Scale, Cue Reactivity), and negative affect (NIH Emotions Toolbox, Negative Affect Reactivity). We have also included a blinding questionnaire to assess the degree to which individuals were blinded to the active versus sham tDCS randomization condition. Breathalyzer tests will be conducted prior to all interviews. Participants who have a BAC > 0.0 will be rescheduled, given snacks and water until their BAC is reduced to < 0.04 in accordance with NIAAA guidelines, and will be provided a taxi voucher.

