During each assessment period (i.e. baseline, end-of-treatment, and 2-month post-treatment follow-ups), self-report measures, and the EEG sessions will occur within one week of the self-report assessment on separate days or on a single day with a break between assessments. All assessments (behavioral, EEG) and treatment sessions will take place in the PCNC. The PCNC has three private assessment rooms to conduct behavioral assessments, as well as an EEG preparation room and shielded acquisition room.

Measure	Description/Purpose	Follow-up		
		Baseline	Post	2-Mo
Locator Form	Contact information for scheduling appointments	X	X	
Edinburgh Handedness scale	Right handedness (inclusion criteria)	X		
Electroencephalography (EEG)	Electrical activity of the brain	X	X	
Demographic form	Age, gender, education, ethnicity	X		
	Marital & employment status, income	X	X	X
Drinking History Questionnaire	Drinking history: onset, prior/current treatment	X	X	X
Form 90	Alcohol & illicit drug use, treatment seeking & AA	X	X	X
Structured Clinical Interview for DSM-IV modified for DSM-5 to include craving item	AUD diagnosis/comorbid SUD diagnoses	X	X	X
Short Inventory of Problems	Brief measure of alcohol-related problems	X	X	X
Penn Alcohol Craving Scale (PACS)	Self-reported craving for alcohol	X	X	X
Impaired Control Scale	Self-reported craving, difficulty controlling craving	X	X	X
International Affective Pictures Series (IAPS)	Behavioral measure cue/negative affect reactivity	X	X	X
UPPS Impulsive Behavior Scale	Urgency, lack of planning, perseveration	X	X	X
Stop Signal Task	Behavioral measure of cognitive control	X	X	X
Mindfulness daily practice tracking sheet	Current mindfulness practices	X	X	X
Breath Counting Tool	Behavioral measure of mindfulness	X	X	X
Toronto Mindfulness Scale	"State" mindfulness	X	X	X
NIH Emotions Toolbox	Social relationships, negative affect, and stress	X	X	X
NIH Cognition Toolbox	Executive function (shifting/attention), memory	X	X	X
Avoidance and Inflexibility Scale	Behavioral avoidance	X	X	X
Regulatory Flexibility Scale	Coping flexibility	X	X	X
Monetary Choice Questionnaire	Delay discounting	X	X	X
Treatment History Form	Assess ongoing treatment and prior/ongoing experience with meditation	X	X	X
Treatment Goals Form	Assess current treatment goal (e.g., controlled drinking, abstinence)	X	X	X
Applied Mindfulness Process Scale	Assess mindfulness skills learned during intervention		X	X

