**Post-Treatment Assessment (up to 5 hours).** After completing the MBRP + tDCS sessions (i.e., up to two weeks after final tDCS/mindfulness session), participants will complete the assessments listed in Table 1 at the PCNC.

**Follow-Up Assessment (up to 2 hours).** At 2 months following completion of MBRP+tDCS, participants will complete the assessments listed in Table 1, with the exception of EEG, at the PCNC.

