## II. *Data Analysis/Statistical Considerations*

**Power analysis and sample size considerations.** We conducted power analyses using effect sizes from a pilot study ( $d=0.64$  and  $d=0.43$  on drinks per drinking day at post- and 2-month follow-up). With desired power  $>0.80$ , a two-tailed  $\alpha < 0.05$ , and three time-points, we will need 70 participants to detect a medium effect of active tDCS + MBRP vs. sham tDCS + MBRP on drinks per drinking day at follow-up. For mediation analyses we will need 74 participants to detect a medium effect. Attrition of 15% is anticipated based on our pilot tDCS study and thus we propose to recruit  $n=86$  participants to allow for some attrition. We anticipate screening up to 350 participants in order to recruit a sample of 86 participants.

**Data Analyses and Missing Data.** The primary study aim is to test the overall efficacy of the active tDCS + MBRP intervention compared to a sham tDCS + MBRP group. We will use maximum likelihood estimation for all analyses, which provides the variance-covariance matrix for all available data and is the preferred method for estimation when some data are missing. Variables associated with missing data and those used in randomization (gender, age, treatment history) will be covaried in all analyses.

**Aim #1: Efficacy Analyses.** All assessment data will be analyzed for outliers and missing cases to detect any bias that might result from differential attrition. The efficacy of active tDCS + MBRP versus sham tDCS + MBRP will be examined using a generalized linear mixed model with drinks per drinking day at the end of treatment and follow-up as the primary outcomes. We hypothesize active tDCS will be associated with significantly larger reductions in drinks per drinking day following treatment, as compared to sham tDCS. Interim analyses to compare sham versus active tDCS treatment efficacy will be conducted in February 2017, after a sufficient number of subjects have been treated, and at the time of submitting our annual progress report to NIH, which will occur in June 2017.

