**Secondary Aim: Mediation Analyses.** Mediation models will be estimated for weekly and post-treatment assessments of mindfulness, inhibitory control, cue reactivity and craving, and negative affect using the product of coefficients method. We will look at self-report and behavioral assessments of each proposed mediator in separate analyses and we will also examine whether latent variables of each construct provide an adequate fit and can be used in the analyses. The mediated effect will be obtained by multiplying coefficients for the regression of the mediators (either separate measures or latent constructs) on treatment condition and for the regression of drinks per drinking day at the 2-month follow-up on the mediators. We will use bootstrapping to obtain 95% confidence intervals of the mediated effect. We hypothesize the effects of active tDCS on drinks per drinking day will be mediated by greater mindfulness, greater inhibitory control and reductions in cue reactivity, craving, and negative affect in the active tDCS group, as compared to sham tDCS.

**EEG Analysis.** EEG analyses will focus on the association between EEG biomarkers (e.g., resting state alpha, theta, beta, and gamma activity, P3 amplitude during tasks) and drinking outcomes, as well as changes in behavioral task performance. Data will be analyzed using MATLAB-based signal processing toolboxes (e.g., EEGLAB, ERPLAB, EEGIFT). We hypothesize significantly increased P3 amplitudes during cognitive inhibition and reduced P3 amplitude in response to alcohol cues in the active tDCS group at post-treatment, as compared to sham tDCS.

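### The P3 comparison between arms is worded at post-treatment with no baseline P3 term, although baseline EEG is recorded; the precision lost depends on a correlation the plan does not give

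*Combined protocol and SAP*

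**What the plan says.** Under the Secondary Aim, Hypothesis 3 opens with "we hypothesize significantly increased amplitude of the P3 (e.g., P300) component of the event-related brain potential (ERP) during cognitive inhibition" and adds a reduced response to alcohol cues, both for the active arm against sham at post-treatment. The EEG Analysis paragraph (Study Data, II. Data Analysis/Statistical Considerations) repeats the contrast; its cue part reads "reduced P3 amplitude in response to alcohol cues in the active tDCS group at post-treatment, as compared to sham tDCS". Neither place names a model, a change score or a baseline term.

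The covariates are set once, under Data Analyses and Missing Data: "Variables associated with missing data and those used in randomization (gender, age, treatment history) will be covaried in all analyses". Baseline P3 is not among them.

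The baseline recording exists. The baseline session includes "completing a battery of self-report and behavioral measures, baseline EEG, and baseline stimulation session", and Table 1 marks the EEG row ("Electrical activity of the brain") at Baseline and Post. At the two-month visit, "participants will complete the assessments listed in Table 1, with the exception of EEG, at the PCNC". The Primary Aim text mentions EEG at two months as well, which disagrees with this but does not affect the post-treatment contrast.

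Hypothesis 3 does refer to change in one other sentence: "Changes in ERPs among those who receive active tDCS with MBRP will be significantly associated with reductions in drinks per drinking day following treatment". That concerns an association within the active arm, not the comparison of arms.

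The Mediation Analyses paragraph describes the treatment-to-mediator step as "the regression of the mediators (either separate measures or latent constructs) on treatment condition", for weekly and post-treatment assessments, again without the mediator's own baseline value.

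**The concern.** A participant's P3 amplitude before treatment is likely to carry information about the amplitude afterwards. If the arms are compared on the post-treatment value alone, stable differences between people stay in the residual variance and the standard error is larger than it need be. Adjusting for the baseline value removes the part that baseline predicts.

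This matters here because the sample is small, there is only one post-treatment EEG, and no power is stated for P3. Because no model is named, a post-only comparison, a change score and a baseline-adjusted comparison all remain open once the data are seen, and their standard errors differ.

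**Working it through.** **The plan's own figures.** No sample size or power is given for P3, so there is none to reproduce. The recruitment target can be followed: the larger stated requirement is 74 (mediation), attrition is 15%, and 74 × 1.15 = 85.1, which rounds up to the stated 86. Expected completers: 86 × 0.85 = 73.1, about 73.

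**Inputs from the documents.** 86 recruited; 15% attrition; two-sided 5% level (stated for drinks per drinking day).

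**Assumptions.** Allocation 1:1, so 36 v 37. Standardised P3 effect d = 0.5: the plan's medium effect is stated for drinking and for mediation, not for P3. Baseline-to-post correlation r is not in the documents, so it is varied from 0.2 to 0.8 and taken as equal in both arms. The covariates common to all analyses are left out of both models; r can be read as the correlation that remains after them.

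**Formulas.** With the post-treatment SD set to 1:

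- Post-treatment only: residual SD s = 1, degrees of freedom 73 − 2 = 71.
- Baseline as covariate: s = √(1 − r²), degrees of freedom 70.
- Noncentrality = d / (s × √(1/36 + 1/37)), where √(1/36 + 1/37) = 0.2341.
- Power is the probability that a noncentral t exceeds the two-sided 5% critical value.
- Equivalent sample = 73 / (1 − r²).

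**Worked example.** Post-only: 0.5 / 0.2341 = 2.136, power 55.8%. With baseline at r = 0.5: s = √0.75 = 0.866, noncentrality 2.136 / 0.866 = 2.466, power 68.2%.

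| Analysis | 1 − r² | Power at d = 0.5 | d detectable at 80% power | Equivalent sample |
|---|---|---|---|---|
| Post-only | 1 | 55.8% | 0.665 | 73 |
| Covariate, r = 0.2 | 0.96 | 57.5% | 0.652 | 76 |
| Covariate, r = 0.3 | 0.91 | 59.8% | 0.634 | 80 |
| Covariate, r = 0.4 | 0.84 | 63.2% | 0.610 | 87 |
| Covariate, r = 0.5 | 0.75 | 68.2% | 0.576 | 97 |
| Covariate, r = 0.6 | 0.64 | 75.0% | 0.532 | 114 |
| Covariate, r = 0.7 | 0.51 | 83.9% | 0.475 | 143 |
| Covariate, r = 0.8 | 0.36 | 94.0% | 0.399 | 203 |

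A normal approximation gives about one point more in the cases compared (57.0% post-only, 69.4% at r = 0.5, 84.9% at r = 0.7), with the same pattern.

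**Why not a raw change score.** Its variance is 2(1 − r), which exceeds 1 when r < 0.5. With 71 degrees of freedom, power is 42.9% at r = 0.3, 55.8% at 0.5, 65.4% at 0.6, 77.6% at 0.7 and 91.5% at 0.8. It is worse than the post-only comparison below r = 0.5, and below covariate adjustment at every value in the table.

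**The case against.** **The plan may not intend a post-only test.** It gives a direction and a visit but no model. Words such as increased and reduced could describe change, and the sentence on ERP changes needs the baseline recording. This stands in part. A reader might infer that the sponsor decided to discard the baseline EEG, and the documents do not support that. They show an omission: the contrast is worded between arms at post-treatment, the covariate list leaves baseline P3 out, and the one explicit use of change is within the active arm. If change was meant, the method is still unstated.

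**The loss may be negligible.** This stands as a limit on size. At r = 0.2 or 0.3 adjustment adds about 2 or 4 points of power. A low r cannot be ruled out: 240 stop-signal trials with about 25% stop trials and about 50% successful inhibition leave roughly 240 × 0.25 × 0.5 = 30 successful stops per session. It is tempting to say that the test is far less sensitive than it could be, or that a real effect would probably be missed for this reason. Either needs an r from the upper part of the range and an assumed effect size.

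**Chance imbalance.** A reader might infer that a chance baseline difference would be taken for a treatment effect. Under randomisation, the unadjusted comparison keeps its 5% type I error, because such imbalance is already in its standard error. A single estimate can be shifted by it, but that is the same imprecision counted above.

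**Mediators.** Those models use weekly as well as post-treatment assessments and may use latent variables, so the P3 figures do not carry over. This stands.

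**Importance.** The EEG paragraph focuses mainly on associations with drinking, and P3 belongs to a secondary aim. This also stands.

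**Conclusion.** The concern holds as a matter of unspecified baseline adjustment. As worded, the P3 contrast makes no use of a baseline value that is already collected. At d = 0.5 and 73 completers the cost ranges from about 2 points of power (r = 0.2) through 12 (r = 0.5) to 28 (r = 0.7) and 38 (r = 0.8). These figures rest on assumed 1:1 allocation, an assumed effect size and an assumed correlation.

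The omission itself is clear from the text; the size of the loss is not. There is no bias and no inflated type I error. The figures say nothing about the primary drinking model, and no magnitude is claimed for the mediators.

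**What to change.** In the EEG Analysis paragraph, add: *Post-treatment P3 amplitude, for each task and condition, will be compared between arms with the participant's baseline P3 from the same task and condition as a covariate.* An equivalent constrained longitudinal model of baseline and post-treatment P3 would also serve. A raw change score should not be the default.

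In the Mediation Analyses paragraph, for observed (non-latent) mediators, weekly or post-treatment, add the mediator's own baseline value to its regression on treatment wherever Table 1 collects it. The Applied Mindfulness Process Scale, for example, has no baseline measurement.

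The cost is two sentences and one degree of freedom per model, with no new data and no extra visits. Latent mediators are left out of this change because they would need a baseline factor and measurement-invariance assumptions, which is a heavier demand on about 73 people.

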## III. *Participant Withdrawal*

If a participant wishes to withdraw from the study all of their information held at the Psychology Clinical Neuroscience Center will be destroyed. They have the right to withdraw their consent or stop participating at any time. They can refuse to answer any question(s) or refuse to participate in any procedure for any reason. Refusing to participate in this study will not result in any penalty or loss of benefits to which they are otherwise entitled.

If they wish to stop participating at any time, they can notify a study team member or [name] at [contact], Monday through Friday, 9am - 5 pm. Alternatively, they can write to her at the PCNC, [name]. All of this information is given to them upon their admittance to the study in their consent form. On the other hand, if the experimenters

decide that a participant is not eligible to continue with the study, their participation may be terminated without their consent.

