### **Space**

Laboratory The PCNC has separate pediatric and adult electroencephalography (EEG) core laboratories (described in detail below), a neurostimulation core laboratory, a large computer core laboratory and a dedicated imaging computer room for data acquisition and analysis for EEG, along with imaging and stimulation laboratories of individual faculty.

Clinical Within the PCNC, three private assessment rooms (all equipped with closed doors and sound screens) are available to research staff.

Office [name] has a private faculty office, as well as four individual Research Assistant offices and access to a conference room.

Meeting Space The PCNC offers multiple group meeting locations to facilitate research. Rooms will accommodate groups from 10 to 40 participants. The rooms are available for investigator and team meetings, research seminars and other research gatherings. Smaller private rooms are available for small group meetings and one-on-one participant and stakeholder interactions.

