**Assessment Protections.** While the nature of the research dictates that data cannot be collected anonymously, additional safeguards will be put in place to protect against breach of confidentiality. Each participant will be assigned a unique ID code at screening. After phone screening, the phone screening form will be destroyed for those who are not eligible. First and last names of those who are screened out will be maintained in order to identify individuals who attempt to re-screen. De-identified demographic information and reasons for ineligibility for those who are ineligible will be recorded in a separate document without identifiers for reporting purposes. Eligible individuals will be scheduled for a baseline assessment session and their phone screening form will be de-identified and only linked to the participant with the participant ID. Contact information for participants who are screened in will be maintained in a password protected file. All assessments for a given participant will be coded with his/her ID code. Questionnaire data will be collected using Mind Research Network COINS system, hosted on a secure Mind Research Network server supporting 128-bit encryption and protected electronically using the most up-to-date security software available. Other data will be retained at the UNM Psychology Clinical Neuroscience Center (PCNC) in locked file cabinets and on password protected electronic files on computers with restricted access. A single master list linking participant names and ID codes will be stored onsite in a separate locked file cabinet, and will only be available to research staff. Further, a Certificate of Confidentiality, which provides additional protection against obligatory release of confidential information, will be obtained from the Department of Health and Human Services prior to participant recruitment.

**EEG Protections.** EEG is considered a safe and noninvasive procedure. There is some risk of seizure during EEG among individuals with seizure disorders, so we will be excluding any participants with a history of seizures or seizure disorder. Participants will be monitored throughout the procedure. If there is any discomfort, the procedure will be discontinued. The PCNC has facilities available to wash off the EEG gel.

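### The withdrawal rule destroys all Center-held data by default, apparently including completed EEG, although the analysis plan relies on all available data and an attrition check

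*Combined protocol and SAP*

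**What the plan says.** Section III, Participant Withdrawal, sets the rule: "If a participant wishes to withdraw from the study all of their information held at the Psychology Clinical Neuroscience Center will be destroyed". The next sentence names two different acts: "They have the right to withdraw their consent or stop participating at any time". For a person who only stops, the section says whom to notify and nothing about data already collected. It also allows the investigators to end someone's participation, again without a data rule.

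Section II, Data Analysis/Statistical Considerations, describes the missing-data approach: "We will use maximum likelihood estimation for all analyses, which provides the variance-covariance matrix for all available data". It adds variables associated with missingness as covariates and promises an attrition check: "All assessment data will be analyzed for outliers and missing cases to detect any bias that might result from differential attrition".

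On storage, Assessment Protections (under Protections Against Risk) makes a split that Privacy of Participants repeats. "Questionnaire data will be collected using Mind Research Network COINS system", which is hosted on a Mind Research Network server. By contrast, "Other data will be retained at the UNM Psychology Clinical Neuroscience Center (PCNC) in locked file cabinets and on password protected electronic files". On EEG, section V says "All assessments (behavioral, EEG) and treatment sessions will take place in the PCNC", and the Space paragraph of Study Resources lists "a dedicated imaging computer room for data acquisition and analysis for EEG". The 2-month visit omits EEG, so the post-treatment recording is the last one. The primary outcome comes from Form 90, a semi-structured interview. No section says where its records are kept.

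**The concern.** Likelihood methods can adjust for dropout that depends on earlier observed values, but only while those values remain in the dataset. A person who leaves after one or two assessments contributes exactly that information, and the attrition check needs it too. A default of destruction removes it for anyone who formally withdraws, and no later sensitivity analysis can restore it.

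The section names withdrawal of consent and stopping participation but gives one data consequence. Two staff members could therefore treat the same departure differently, one erasing the record and the other keeping it as partial data.

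At stake are completed EEG recordings for Hypothesis 3, part of the description of who left and from which arm, and possibly, depending on where Form 90 is kept, the primary contrast.

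**Working it through.** 1. **What the rule reaches.** It covers information held at the Center.
   - Questionnaire data: on COINS, hosted elsewhere, so outside the rule as worded.
   - EEG: not questionnaire data, so it belongs with the other data kept at the Center. It is recorded there, and the computer room for acquiring and analysing it is there. That is a strong inference, but no sentence names where EEG is stored.
   - Form 90: an interview, storage not stated. Undetermined.
   - People lost to follow-up without withdrawing, and people removed by the investigators: not covered by the sentence.

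2. **How many people.** The plan's target of 86 can be recovered as 74 (the mediation requirement) × 1.15 = 85.1, rounded up. The same section anticipates 15% attrition: 86 × 0.15 = 12.9, about 13. Section VIII (Participant Compensation) cites follow-up of 87.5% or better: 86 × 0.125 = 10.75, about 11. Neither figure says how much of the loss is formal withdrawal, so the number erased lies between 0 and about 13.

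3. **EEG precision.** Assume every participant would have a post-treatment EEG, with erasures spread evenly over equal arms. The standard error of the P3 contrast then grows by √(86 / (86 − erased)).
   - 3 erased: √(86/83) = 1.018, about 2%.
   - 6 erased: √(86/80) = 1.037, about 4%.
   - 13 erased: √(86/73) = 1.085, about 8.5%.

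   The last line needs all 13 leavers to complete the post-treatment EEG and then withdraw formally. If the other leavers had gone before that visit, the first two lines barely change: √(76/73) = 1.020 and √(79/73) = 1.040.

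4. **Primary outcome, only if Form 90 is held at the Center.** If it is on COINS, every figure here is 0. This is an illustration by simulation with assumed inputs: 43 per arm, three visits correlated 0.6, SD 1, normal data, 20,000 trials per scenario. There is no true effect. Leaving depends on post-treatment drinking in the active arm only (logit −1.6 + 1.2 × post-treatment value; logit −2.2 in sham), giving 22% and 10% leaving, about 13.8 people. The table shows the shift caused by destroying rather than keeping data. It favours active tDCS here; the standard error is about 0.19 SD.

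| Leave after post-treatment visit | Formally withdraw | Shift, end of treatment | Shift, 2 months |
|---|---|---|---|
| all | all | 0.14 | 0.05 |
| half | all | 0.08 | 0.03 |
| half | 25% | 0.02 | 0.01 |
| none | all | 0 | 0 |

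   With the pilot effects (0.64 and 0.43) as truth, and half leaving after the visit and 25% withdrawing formally, the apparent end-of-treatment benefit changes by +0.01, −0.01 or −0.02. These are for drinking-related leaving in active only, equally in both arms, or in sham only. At 2 months each change is below 0.01. Expected leavers differ across these three cases (about 9.9, 11.4 and 13.8), so they show that the sign is open, not a clean comparison of direction.

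   Keeping the data does not cure everything. With half leaving before the post-treatment visit and no true effect, 0.06 SD of end-of-treatment bias remains, because those values were never collected.

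**The case against.** The strongest reply is that the rule may touch few people and little of importance. Formal withdrawal may be rare, and the plan's 15% is attrition of every kind. Section I of Study Data (Data Management) speaks of online data collection forms and of COINS safeguards against entry errors. That makes it plausible, though not proven, that Form 90 is entered there and survives. Questionnaire baselines on COINS would also survive, so the attrition check would be thinned rather than defeated. Participants may refuse any procedure without withdrawing, and Hypothesis 2 uses session attendance as a dose measure, which presupposes keeping people who miss sessions. Adverse events already reported to the IRB remain on record. Erasure is also a real privacy promise to people disclosing alcohol and illicit drug use. Finally, section III says the consent form carries this information; that form is not in the public document and may be narrower.

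Most of this stands, and it limits the size of the point. It does not answer it. The rule as written still makes destruction the default for Center-held records, still fails to separate stopping from withdrawing, and still sits against an analysis section that counts on partial records. If the consent form is narrower, section III should be brought into line with it.

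A reader might infer that drinks per drinking day will be erased or biased. The documents do not support that, because they do not say where Form 90 is stored. A reader might also infer that everyone in the 15% is erased. The sentence covers only those who wish to withdraw.

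**Conclusion.** The point holds as a conflict between the withdrawal rule and the analysis plan. Any loss under the rule would be irreversible, but whether there is any loss depends on formal withdrawals, and that count may be 0.

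- **EEG:** a modest loss of precision on a secondary aim, about 2% to 4% in standard error for 3 to 6 erased recordings and 8.5% at the extreme of 13. This rests on the inference that EEG is held at the Center.
- **Primary outcome:** conditional. Zero if Form 90 is on COINS; otherwise probably small and of unknown sign. A shift as large as 0.14 SD needs strongly one-sided, drinking-related leaving, all of it after the post-treatment visit and all of it formal. The figures depend on an assumed correlation, an assumed dropout model and normal data, whereas the plan specifies a generalized linear mixed model.
- **People who leave before the post-treatment visit:** their post-treatment value is missing under either rule, so retention protects only their earlier records.

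This is a cheap improvement worth making. It is not evidence that the primary analysis is invalid.

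**What to change.** Amend section III and the matching consent wording so that:

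1. coded data collected before withdrawal are kept and analysed in the assigned arm unless the participant explicitly asks for deletion;
2. stopping sessions is separated from withdrawing consent, and the existing post-treatment and 2-month assessments are still offered to those who only stop sessions;
3. where deletion is requested, only a non-identifying count by arm is kept and reported, while for everyone else who leaves, the arm, date, reason and safety records are kept;
4. the text states whether Form 90 and COINS data fall under the deletion rule.

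The cost is one wording amendment through the IRB, with no new visits or measures. The downside is that participants who want erasure must ask for it. Those already consented keep the existing promise unless re-consented.
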